7.1.1 Disposition

For each cohort enrolled into the study, patient disposition details will be presented by treatment group and overall. Disposition details include number Screened, number and percentage Randomised (ITT population), Treated (Safety population), Completed, Discontinued, and the Primary Reason for Discontinuation (Tables 14.1.1 and 14.1.2). For

each cohort, discontinuations from the study will be listed by treatment group and patient with the date of discontinuation, primary reason and the corresponding AE number if applicable (Listing 16.2.1.5).

7.1.2 Demographics.

For each cohort in the Safety population, patient demographic details (age, sex, race and ethnicity) will be summarised according to treatment group and overall (Table 14.1.3).

7.1.3 Protocol Deviations

For each cohort, protocol deviations will be listed by treatment and patient, showing the deviation details (Listing 16.2.1.4).

7.1.3 Concomitant Medication

For each cohort, prior and concomitant medications will be summarised by treatment group and overall according to the WHO drug dictionary ATC code levels 2 and 4 (Tables 14.1.4 and 14.1.5).

7.1.4 Medical History.

For each cohort, medical history details will be summarised according to the MedDRA system organ class and preferred term by treatment group and overall (Table 14.1.6). Height, weight and BMI will also be summarised (Table 14.1.7).

7.1.5 Drug Administration.

For each cohort, compliance with study drug administration will be summarised by treatment group as both percentage compliance and classified according to whether patients were less than or equal to/greater than 80% compliant (Table 14.1.8).

7.2 Pharmacodynamics

For each cohort, the levels of neurotoxic proteins in plasma and CSF collected at hourly intervals during the 6 hour post dose confinement, the actual values and change from baseline and percentage change from baseline will be summarized by treatment group.

7.2.1.1 Target Engagement - CSF

The target engagement CSF variables include: A β -40, A β -42, sAPP α , sAPP β , t-tau, p-tau-181 and a-SYN and are summarised in Tables 14.2.1.1.1 – 14.2.1.1.7.

Subsequently, the results from the Within group ANOVA model of the percentage changes from Baseline (between Baseline Day 0 Pre-dose 0h and Day 25 Pre-dose 0h) will be presented, together with Maximum Percentage Change over 6h (Day 25) from Baseline (Day 25 Pre dose 0h) (Model terms – Table 14.2.1.2; Model estimates – Table 14.2.1.3) and plotted as treatment estimates (Figures 14.2.1.1, Template 1).

Additionally, the percentage change from baseline (Day 25 Pre-dose 0h - Day 0 Pre-dose 0h) and the Maximum Percentage Change over 6h (Day 25) from Baseline (Day 25 Pre-dose 0h) will be analysed for Between group differences. This will initially involve analysing the change from baseline differences between the Placebo treatment groups in Part 1 and the 80mg patient groups from Part 1 in both the AD and PD cohorts, and subsequently the differences between the PD Placebo patients from Part 1 and the 5mg, 10mg, 20mg and 40mg Parkinson patient groups from Part 2; and repeating the PD Placebo versus PD 80mg

comparison (Model terms – Table 14.2.1.2; Model estimates – Table 14.2.1.3) and plotted as treatment estimate differences (Figures 14.2.1.2, Template 2).

Furthermore, the percentage change from Baseline (Day 25 Pre-dose 0h) for each of the 6 hourly assessments will be analysed using a Repeated measured mixed model (RMMM) and will be presented in Tables 14.2.1.4 and 14.2.1.5 for Within and Between treatment group model terms and estimates, respectively, together with corresponding plots (Figures 14.2.1.3, Templates 3 and 4, respectively).

On completion of the two Part 1 cohorts, the target engagement CSF biomarkers will be evaluated and this will inform a decision about which should be assayed and statistically analysed after Part 2 has been completed.

7.2.1.2 Pathway engagement – CSF

The pathway engagement CSF variables include: NfL, GFAP, Complement C3, YKL40, sTREM2, SNAP25, Synaptotagmin, Neurogranin and Beta-trace protein and are summarised in Tables 14.2.2.1.1 – 14.2.2.1.9.

Subsequently, the results from the Within group ANOVA model of the percentage changes from Baseline (between Baseline Day 0 Pre-dose 0h and Day 25 Pre-dose 0h) will be presented, together with Maximum Percentage Change over 6h (Day 25) from Baseline (Day 25 Pre dose 0h) (Model terms – Table 14.2.2.2; Model estimates – Table 14.2.2.3) and plotted as treatment estimates (Figures 14.2.2.1, Template 1).

Additionally, the percentage change from baseline (Day 25 Pre-dose 0h - Day 0 Pre-dose 0h) and the Maximum Percentage Change over 6h (Day 25) from Baseline (Day 25 Pre dose 0h) will be analysed using a Between group ANOVA model. This will initially involve analysing the change from baseline differences between the Placebo treatment group from Part 1 and the 80mg Parkinson patient group from Part 1, and subsequently the differences between the Placebo from Part 1 and the 5mg, 10mg, 20mg and 40mg Parkinson patient groups from Part 2 (Model terms – Table 14.2.2.2; Model estimates – Table 14.2.2.3) and plotted as treatment estimate differences (Figure 14.2.2.2, Template 2).

Furthermore, the percentage change from Baseline (Day 25 Pre-dose 0h) for each of the 6 hourly assessments will be analysed using a Repeated measured mixed model (RMMM) and will be presented in Tables 14.2.2.4 and 14.2.2.5 for Within and Between treatment group model terms and estimates, respectively, together with corresponding plots (Figures 14.2.2.3, Templates 3 and 4, respectively).

On completion of the two Part 1 cohorts, the pathway engagement CSF biomarkers will be evaluated and this will inform a decision about which should be assayed and statistically analysed after Part 2 has been completed.

7.2.2.1 Target Engagement - Plasma

The target engagement plasma variables include: A β -40, A β -42, t-tau and p-tau-181 and are summarised in Tables 14.2.3.1.1 – 14.2.3.1.4.

These variables are analysed as for the CSF variables:

Within group ANOVA model: Model terms – Table 14.2.3.2; Model estimates – Table 14.2.3.3) and plotted as treatment estimates (Figures 14.2.3.1, Template 1).

Between group ANOVA model: Model terms – Table 14.2.3.2; Model estimates – Table 14.2.3.3) and plotted as treatment estimate differences (Figure 14.2.3.2, Template 2).

Repeated measured mixed model (RMMM) – Within Group: Model terms – Table 14.2.3.4 and Model Estimates Table 14.2.3.5 and Between group also in Tables 14.2.3.4 and 14.2.3.5, respectively, together with corresponding plots (Figures 14.2.3.3, Templates 3 and 4, respectively).

On completion of the two Part 1 cohorts, the target engagement plasma biomarkers will be evaluated and this will inform a decision about which should be assayed and statistically analysed after Part 2 has been completed.

7.2.2.2 Pathway Engagement - Plasma

The pathway engagement plasma variables include: NfL and GFAP and are summarised in Tables 14.2.4.1.1 – 14.2.4.1.2.

These variables are analysed as for the CSF variables:

Within group ANOVA model: Model terms – Table 14.2.4.2; Model estimates – Table 14.2.4.3) and plotted as treatment estimates (Figures 14.2.4.1, Template 1).

Between group ANOVA model: Model terms – Table 14.2.4.2; Model estimates – Table 14.2.4.3) and plotted as treatment estimate differences (Figure 14.2.4.2, Template 2).

Repeated measured mixed model (RMMM) – Within Group: Model terms – Table 14.2.4.4 and Model Estimates Table 14.2.4.5 and Between group also in Tables 14.2.4.4 and 14.2.4.5, respectively, together with corresponding plots (Figures 14.2.4.3, Templates 3 and 4, respectively).

On completion of the two Part 1 cohorts, the pathway engagement plasma biomarkers will be evaluated and this will inform a decision about which should be assayed and statistically analysed after Part 2 has been completed.

7.2.3 Efficacy - Functional/Cognition

Prior to any formal statistical analyses of the cognitive and functional endpoints, each question, sub-domain and total score will be descriptively summarised and evaluated. Subsequently, formal statistical analysis will only be performed and reported if any notable change from baseline is observed in the descriptive summaries. This process will be repeated at each analysis stage, i.e. Part 1 PD, Part 1 AD and Part 2 PD database locks.

Depending on the outcome of these original evaluations:

All Cohorts: every patient is evaluated using the MMSE and WAIS-IV: MMSE

The total score and absolute and standardised change from baseline for the MMSE functional cognitive measure or any sub-score (after initial evaluation) will be summarised by treatment group (Table 14.3.1.1). Scores from the individual questions will also be listed. The results from the Within treatment group ANOVA on the change from baseline will also be presented in Table 14.3.1.2 (model terms) and Table 14.3.1.3 (model estimates, LS means \pm 95% CIs) and plotted as treatment estimates (Figure 14.3.1.1, Template 1).

Additionally, the change from baseline differences between the Placebo treatment groups in Part 1 and the 80mg patient groups from Part 1 in both the AD and PD cohorts, and subsequently the differences between the PD Placebo patients from Part 1 and the 5mg, 10mg, 20mg and 40mg Parkinson patient groups from Part 2; repeating the PD Placebo versus PD 80mg comparison will be analysed. The results from these Between treatment group ANOVAs on the change from baseline will also be presented in Table 14.3.1.2 (model terms) and Table 14.3.1.3 (model estimates, LS means $\pm 95\%$ CIs differences) and plotted as treatment estimate differences (Figure 14.3.1.2, Template 2).

WAIS-IV

This will be summarised (Table 14.3.2.1) and analysed in a similar manner to the MMSE with results from the Within treatment group ANOVA on the change from baseline being presented in Table 14.3.2.2 (model terms) and Table 14.3.2.3 (model estimates, LS means $\pm 95\%$ CIs) and plotted as treatment estimates (Figure 14.3.2.1, Template 1).

Additionally, the change from baseline differences between the Placebo treatment groups in Part 1 and the 80mg patient groups from Part 1 in both the AD and PD cohorts, and subsequently the differences between the PD Placebo patients from Part 1 and the 5mg, 10mg, 20mg and 40mg Parkinson patient groups from Part 2; repeating the PD Placebo versus PD 80mg comparison will be analysed. The results from these Between treatment group ANOVAs on the change from baseline will also be presented in Table 14.3.2.2 (model terms) and Table 14.3.2.3 (model estimates, LS means $\pm 95\%$ CIs differences) and plotted as treatment estimate differences (Figure 14.3.2.2, Template 2).

Parkinson Patients – Parts 1 and 2

MDS-UPDRS

The MDS-UPDRS total score and four individual domain scores (Non Motor Aspects of Experiences of Daily Living; Motor Aspects of Experiences of Daily Living; Motor Examination; Motor Complications) or any sub-score (after initial evaluation) will be summarised (Tables 14.3.3.1) and analysed in a similar manner to the MMSE. The results from the Within treatment group ANOVA on the change from baseline and Between treatment group ANOVA differences (Part 1: Placebo vs 80mg; Part 2: Placebo vs 5mg, 10mg, 20mg, 40mg and 80mg) will be presented in Tables 14.3.3.2 (model terms) and Tables 14.3.3.3 (model estimates, LS means $\pm 95\%$ CIs) and plotted as treatment estimates (Figures 14.3.3.1 (Template 1) and 14.3.3.2 (Template 2), for Within and Between estimates, respectively).

Furthermore, the Hoehn and Yahr scores will be categorically summarised by treatment group and visit in both Parts 1 and 2 (Table 14.3.3.4).

Alzheimer Patients – Part 1 only

ADAS-cog

The ADAS-cog 14, 11, 6, 3 total score or any sub-score (after initial evaluation) will be summarised (Table 14.3.4.1) and analysed in a similar manner to the MMSE with results from the Within treatment group ANOVA on the change from baseline and change from baseline Between treatment group ANOVA difference between Placebo and 80mg AD patients being presented in Table 14.3.4.2 (model terms) and Table 14.3.4.3 (model estimates, LS means $\pm 95\%$ CIs) and plotted as treatment estimates (Figures 14.3.4.1 (Template 1) and 14.3.4.2 (Template 2), respectively).

CDR

The CDR scale will be categorically summarised by item (Memory, orientation, judgement and problem solving, community affairs, home and hobbies, and personal care) and overall Global summary score by visit (Table 14.3.5). Additionally, the sum of boxes score will also be summarised and analysed following initial evaluation as described for the ADAS-cog (Tables 14.3.5.1, 14.3.5.2 and 14.3.5.3, for descriptive summaries, model and treatment estimates, respectively, together with corresponding Figures 14.3.5.1 (Template 1) and 14.3.5.2 (Template 2)).

7.3 Safety.

For consistency with the pharmacodynamic and cognitive/functional summaries and analyses and for comparative purposes, safety data from the Placebo and 80mg Part 1 PD patients will be combined with the data collected from the PD patients in Part 2. Consequently, all safety summaries will include: the Placebo and 80mg PD patients for the Part 1 PD cohort analysis report; Placebo and 80mg AD patients for the Part 1 AD cohort analysis report; and, for the Part 2 analysis report, Placebo and 80mg PD patients from Part 1 together with the 5mg, 10mg, 20mg and 40mg PD patients from Part 2.

7.3.1.1 Adverse Event Overview.

For each cohort, all adverse events and serious adverse events will be listed by treatment group and patient (Listing 16.2.1.1).

For each cohort and treatment group, an overview summary will display the frequency, number and percentage of patients, with any adverse event, pre-treatment sign and symptom (PTSS) and treatment emergent adverse events (TEAEs). Additionally, the table will include the number of TEAEs classed by CTCAE Grade (mild, moderate, severe, life threatening, death), relationship to drug (unrelated, possibly related, related), by severity evaluation (mild, moderate, severe), and overall numbers related to a study procedure, AEs leading to discontinuation of study IMP, SAEs, and death (Table 14.4.1.1).

7.3.1.2 Adverse Events (AEs) and Serious Adverse Events (SAEs).

For each cohort and treatment group, the number and percentage of patients with PTSS will be summarised by SOC and PT (Table 14.4.1.2). Similar tables will be presented for TEAEs (Table 14.4.1.3), Related TEAEs (14.4.1.4), TEAE and CTCAE grade (14.4.1.5.1 – 14.4.1.5.5), SAEs (14.4.1.6, TEAEs leading to discontinuation of study IMP(14.4.1.7) and TEAEs leading to death (14.4.1.8).

7.3.2 Laboratory Data.

For each cohort and treatment, laboratory data will be presented as normal summaries, actual values and change from baseline according to profile (Biochemistry: Tables 14.4.2.1.1 – 14.4.2.1.14; Haematology: Tables 14.4.2.2.1 – 14.4.2.2.10; Coagulation: Table 14.4.2.3; Urinalysis: Tables 14.4.2.4). The data will also be presented as Categorical ('Not Done', 'Abnormal NCS', 'Abnormal CS' and 'Normal') summaries by Treatment group according to profile (biochemistry, haematology and urinalysis) and visit as Tables 14.4.2.5. Urinalysis variables will also be presented as Categorical summaries (according to type) by Treatment group and visit as Tables 14.4.2.6.1 – 14.4.2.6.20. Scatter plots of pre-treatment vs. post-treatment values for all haematology and clinical chemistry variables will be displayed (Figures 14.4.2, Template 5).

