In this study, we want to find out if the animal Posiphen data can be replicated in humans and show target and pathway engagement in CSF. Target engagement means that Posiphen would lower and normalize the levels of neurotoxic proteins in CSF. Pathway engagement means that Posiphen would increase levels of neurotransmitters, neurotrophic factors, and lower levels of inflammatory and neurodegeneration markers in both AD and PD patients. By examining all these factors in early AD and PD patients, we will specify the biomarkers that change with Posiphen treatment, which will be used in later phase studies. Additionally, we will assess function and cognition, so we can make sure that Posiphen has no deleterious effect and potentially identify any improvement. Collectively, these endpoints will help assess the efficacy of Posiphen and drive it to late phase clinical studies.

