5.2.2 Efficacy - Functional/Cognitive Measures

Patients will complete the appropriate questionnaires at Baseline and Day 25 (Confinement). For each, the Total score and, where appropriate the item/domain scores, will be calculated, and the Change from Baseline derived. Actual scores and Effect sizes ($(X_{\text{Base}} - X_{\text{Day25}})/SD$) will be presented.

MMSE is a 30 point test that is widely used for cognitive function that includes tests of orientation, attention, memory, language and visual-spatial skills.

WAIS-IV is a test to assess cognitive ability in adults which helps to examine the relationship between intellectual function and memory in seven subtests: Spatial Addition, Symbol Span, Design Memory, General Cognitive Screener, Logical Memory (I & II), Verbal Paired Associates (I & II), and Visual Reproduction (I & II). Performance is reported as five Index Scores: Auditory Memory, Visual Memory, Visual Working Memory, Immediate Memory, and Delayed Memory. Patients will be scored on the number of correct items from images and words shown in the space of two minutes.

MDS-UPDRS has four parts: Part 1 – non-motor experiences of daily living (13 items), Part 2 - motor experiences of daily living (13 items), and Part 3 – motor examination (20 scores based on 18 items plus Hoehn and Yahr Stage) and Part 4 – motor complications (6

questions). Each item is scored on a scale of 0 (normal) to 4 (severe). Scores from each part of the scale are combined to provide a total score.

ADAS-Cog14 is a test to evaluate cognition and differentiates between normal and impaired cognitive functioning by using a number of tests to assess memory, language and comprehension. Different Word lists were used in different countries to allow for language differences but validated versions were always used and always presented in the correct and standardised manner.

CDR is a global summary to identify the overall severity of dementia from domains; Memory, Orientation, Judgement and Problem solving, Community Affairs, Home and Hobbies and Personal care, each of which is rated on a 5 point score.

Table 4: Clinical Function and Cognitive Endpoint Scoring

Efficacy		Score Range (units)	Scale Direction
Cognitive Function Tests			
WAIS-IV	Total Score	Scaled Score 0 - 100	High score best
ADAS-cog14 (14 items)	Total Score (Count incorrect items)	0 - 90	Low score best (0=All correct)

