5.6 Other Definitions

Baseline, Study Day and Event Duration are specifically defined as:

Baseline

Two baselines are defined:

- 1 Last assessment prior to first dose of study IMP on Day 0.
- 2 At 0 hours on Day 25 of the Confinement visit

Study Day

Study Day = (Date of event - first dose of study IMP) + 1.

Event Duration

Event Duration= (Date of resolution – Date of onset) + 1

6. Statistical Methods.

This statistical analysis plan specifies the requirements for the analysis and reporting of all data collected during the study.

All analyses and data reporting procedures will be undertaken using SAS® v9.4 in a Windows version 10 operating system environment.

The descriptive statistics produced will account for the nature and distribution of the data collected. For continuous variables (actual and percentage change from baseline), data will be presented as number (n), mean, median, standard deviation, and range. For discrete variables (Incidence, Response outcome) data will be presented as frequencies and proportions and the denominator will be the number of patients available.

Data collected from patients in each of the three cohorts (Part 1 AD, Part 1 PD, Part 2 PD) will be derived and summarised as described in section 5 and analysed according to the defined analysis population in section 4.

All comparisons of primary interest performed in Part 1 and Part 2 involve changes from baseline (Within treatment group). The null hypothesis throughout is that there is no difference between the Day 25 end of treatment and Pre-treatment baseline (H0. $X_{end}=X_{base}$, H1. $X_{end} \neq X_{base}$).

Between treatment groups comparisons are also possible (but of secondary interest due to the small sample size). Here the null hypothesis is that there is no difference between any of the treatment groups at the end of treatment (H0. Placebo= $X_{5mg}=X_{10mg}=X_{20mg}=X_{40mg}=X_{80mg}$, H1. Placebo $\neq X_{5mg} \neq X_{10mg} \neq X_{20mg} \neq X_{40mg} \neq X_{80mg}$).

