6.2 Functional Cognitive Endpoints

Prior to any formal statistical analyses of the cognitive and functional endpoints, each question, sub-domain and total score will be descriptively summarised and evaluated. Subsequently, formal statistical analysis of individual questions will only be performed and reported if any notable change from baseline is observed in the descriptive summaries. This process will be repeated at each analysis stage, i.e. Part 1 PD, Part 1 AD and Part 2 PD database locks.

For the Part 1 AD and Part 1 PD cohorts, the variables will be analysed using an ANOVA model of the Change from Baseline (Day 25 - Day 0). This will include Treatment group as a fixed effect, and LSmeans (with 95% CI) for this effect will be presented (Within group) together with Effect sizes ($(X_{Day\ 25} - X_{Base})/SD$). Between treatment group differences will also be presented for the comparison between Placebo and 80mg but interpreted cautiously.

For the Part 2 PD cohort with 4 treatment dose groups (5, 10, 20, 40mg) a similar ANOVA will be employed. However, the data from the Part 1 PD patients will also be included from both the Placebo and 80mg patient groups and combined with the Part 2 Parkinson patient data. Within and Between group ANOVA model analyses will then be employed in a similar manner to Part 1. However, in the Part 2 report, treatment group differences will include Placebo (from Part 1) versus each of the five active treatment groups, namely 5mg, 10mg, 20mg and 40mg from Part 2, and 80mg group from Part 1.

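### SAP 7.2.3, read literally, makes formal analysis of functional and cognitive total and domain scores depend on an undefined notable change, while SAP 6.2 restricts that condition to individual questions

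*SAP*

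**What the plan says.** SAP 6.2 (Statistical Methods) first has every question, sub-domain and total summarised descriptively. It then says "formal statistical analysis of individual questions will only be performed and reported if any notable change from baseline is observed". For the Part 1 cohorts it continues, with no condition, that "the variables will be analysed using an ANOVA model of the Change from Baseline", giving LS means, 95% CIs, effect sizes and a placebo versus 80 mg difference. Part 2 is handled in the same way.

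SAP 7.2.3 (Presentation) opens with nearly the same paragraph, but the restriction to individual questions is absent: "formal statistical analysis will only be performed and reported if any notable change from baseline is observed in the descriptive summaries". The MMSE, WAIS-IV, MDS-UPDRS, ADAS-cog and CDR output is then introduced by "Depending on the outcome of these original evaluations". For the CDR, "the sum of boxes score will also be summarised and analysed following initial evaluation as described for the ADAS-cog".

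Both sections repeat the decision at each of three database locks (Part 1 PD, Part 1 AD, Part 2 PD). SAP Section 7 says each cohort is unblinded as it completes.

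On descriptive output, SAP 5.2.2 promises "Actual scores and Effect sizes", and SAP Section 6 says that for continuous variables "data will be presented as number (n), mean, median, standard deviation, and range".

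On purpose, Protocol Section 2 says "we will assess function and cognition, so we can make sure that Posiphen has no deleterious effect", and Protocol 4.2 predicts that cognition and function will stay stable. SAP 2.1.2 adds that the tests will supply variability estimates for future power calculations.

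**The concern.** Two sections of one SAP give different rules for the same scores. Under 6.2 the ANOVA for a total score is always run. Under 7.2.3 it is run only if someone judges a change notable in unblinded summaries of the same data. Neither document gives a threshold, a direction or a decision-maker. Neither says which treatment group counts, or whether one notable score opens only itself or all scores.

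The quantity screened is change from baseline, which SAP Sections 2 and 6 name as the comparison of primary interest. The data would therefore decide whether their own interval is reported. The result most likely to lose its interval and placebo contrast is a flat one, which the protocol expects and would use to support a statement of no deleterious effect. In a group of 10, a mean near zero without an interval says little about what has been excluded.

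**Working it through.** **1. The texts side by side.**

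| Item | SAP 6.2 | SAP 7.2.3 |
|---|---|---|
| Summarised first | question, sub-domain, total | question, sub-domain, total |
| Formal analysis conditional for | individual questions | no restriction stated |
| ANOVA of totals and domains | unconditional | follows a conditional lead-in |
| Definition of notable | none | none |

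Both cannot be followed for a total score that shows no notable change.

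**2. How often the condition would suppress an analysis.** The SAP states no figure to reproduce, so this is an illustration. From the documents: 10 active and 4 placebo patients per Part 1 cohort (SAP 3.3); six groups and 54 patients in Analysis 3 (SAP Section 7). Assumed: a score opens when |mean change|/SD in a group exceeds g; g = 0.2, 0.3 or 0.5; normal data; no true change.

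For one group of size n, P(shut) = P(|t with n−1 df| ≤ g√n). If either Part 1 group can open a score, the two values multiply. If any of six Analysis 3 groups can, P(shut) = (n=10 value)^5 × (n=4 value).

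| g | n=10 | n=4 | Either Part 1 group | Any of six groups |
|---|---|---|---|---|
| 0.2 | 0.457 | 0.284 | 0.130 | 0.006 |
| 0.3 | 0.632 | 0.409 | 0.259 | 0.041 |
| 0.5 | 0.852 | 0.609 | 0.519 | 0.273 |

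So 13%, 26% or 52% of Part 1 scores get no formal analysis on the either-group reading. With a true 0.5 SD worsening at 80 mg and none on placebo (noncentral t for the active group), 4%, 10% or 29% would still not be analysed.

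**3. If one notable score opens all.** The seven PD scores are MMSE, WAIS-IV, MDS-UPDRS total and its four parts. Simulated at g = 0.5 in Part 1 with equal between-score correlation, every score stays shut in about 1% of cases (correlation 0), 4% (0.5) or 9% (0.7).

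**4. Effect on what is reported.** On the either-group reading with no true change, simulated coverage of the 80 mg within-group 95% CI among reported analyses is 94.3% at g = 0.2 and 89.7% at g = 0.5. Over all planned analyses, reported or not, it is 95%.

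**5. What the omitted intervals would show.** With treatment as the only stated effect, the Part 1 error df are 14 − 2 = 12 and t(0.975) = 2.179. The half-widths are:
- 80 mg within group: 2.179/√10 = 0.69 SD
- 80 mg versus placebo: 2.179 × √(1/10 + 1/4) = 1.29 SD

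**The case against.** The strongest reply is that this is a drafting slip. The two paragraphs differ mainly by the phrase restricting the condition to individual questions, and 6.2 is the methods section. Elsewhere in 7.2.3 the qualifier about initial evaluation follows the mention of sub-scores for MMSE, MDS-UPDRS and ADAS-cog, while totals and the four MDS-UPDRS parts are named first with numbered ANOVA tables. Read strictly, the conditional lead-in would even cover the descriptive tables and the Hoehn and Yahr summary, which is implausible. This is a fair reading and may well be the intent, but the text does not settle it, and the CDR sum of boxes, a total, carries the qualifier directly.

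Second, little information is lost. With no covariate, LS means are raw means and the error term is the pooled SD, s² = (9·s_A² + 3·s_P²)/12 in Part 1, where s_A and s_P are the 80 mg and placebo SDs of change. Every omitted CI then follows from n, mean and SD of change. This stands wherever those summaries are presented. What is lost is reporting, since a reader would have to do the calculation.

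Third, the endpoints are exploratory, Protocol 6.5 calls the statistical comparisons descriptive, the SAP treats between-group results as secondary, and descriptive SDs meet the variability aim in SAP 2.1.2. This limits the weight of the point but does not resolve the contradiction.

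A reader might also infer that the condition raises the false-positive rate of the planned analyses, or that a large and known share of analyses will disappear. The documents support neither. The per-test rate over all planned analyses stays at 5%; only the reported subset is distorted. The share depends on a threshold and an opening rule that the SAP does not give, and its word *any* favours the readings in which little is suppressed.

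**Conclusion.** The conflict between 6.2 and 7.2.3 is real, and notable is undefined in both. Taken literally, 7.2.3 makes formal analysis of totals and domains depend on the data being analysed, and drops intervals and placebo contrasts when function looks stable.

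The size cannot be fixed from the SAP. The range is 13% to 52% of Part 1 scores if either group can open a score, against about 1% to 9% at a 0.5 SD threshold if any one score opens all. These figures rest on assumed thresholds, normal data, no true change and, for the last range, equal correlations of 0 to 0.7. That range is not an upper limit, because higher correlation would raise it. Real scores are bounded integers, and the MDS-UPDRS total is the sum of its parts.

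It would go too far to conclude that the sponsor intends to withhold total-score results, or that harm would be hidden: descriptive results are planned, and the intervals can be rebuilt from them. The point should be corrected before unblinding, but it does not threaten the trial's primary aims of safety, tolerability and pharmacokinetics.

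**What to change.** In SAP 7.2.3, restrict the condition to individual questions, as 6.2 does. Remove the lead-in "Depending on the outcome of these original evaluations" and, for the CDR sum of boxes, the phrase that makes its analysis follow an initial evaluation.

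State that at each lock LS means and between-group differences, with 95% CIs, are always reported for the MMSE total, WAIS-IV, MDS-UPDRS total and four parts, ADAS-cog 14, 11, 6 and 3 totals, and CDR sum of boxes.

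For individual questions, either define notable numerically before the first cohort is unblinded, including which group counts and what one notable score opens, or label those analyses post hoc.

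The cost is SAP wording and a few more tables; the models, table numbers and figures for totals and domains are already specified. No patients, visits or assays change. The downside is that more wide, null intervals will be shown (the 0.69 SD and 1.29 SD half-widths above), making plain how little groups of 10 and 4 can exclude.
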